### **6.4 Agent Distribution**

Agents will only be released by NCI, DCP after documentation of IRB approval of the DCP-approved protocol and consent is provided to DCP and the collection of all Essential Documents is complete (see DCP website for description of Essential Documents). These Essential Documents should be submitted to the CLO for processing. When a site has submitted all of the required documents, the DCP's Regulatory Contractor will issue Drug Shipment Authorization for that site. No study agent will be shipped to a site until the Drug Shipment Authorization has been issued and a study initiation visit or teleconference has been completed.

The request for study agent to be shipped to each site will be generated by the CLO using the DCP Clinical Drug Request form (NIH-986). At the time of study initiation, the CLO will request complete shipping contact information for the site's investigational pharmacy. If the site does not have an investigational pharmacy, the complete shipping contact information for the person responsible for study agent accountability at the site will be requested. DCP guidelines require that the agent be shipped directly to the institution or site where the agent will be administered. DCP does not permit the transfer of agents between institutions (unless prior approval from DCP is obtained). The CLO will submit study agent requests to:

[name]  
MRIGlobal  
DCP Repository  
[name]  
[name]  
[contact]  
[contact]  
Emergency [contact]

Participants in this study are randomized on a 2:1 ratio of ACTOplus met® XR:placebo using permuted blocks of 3. Prior to study activation, study statisticians will provide MRIGlobal with a sequential list of 5-digit randomization numbers divided into blocks of 3. Each randomization number will be linked to a treatment assignment - active study agent (ACTOplus met® XR) or placebo. Within each block of 3 randomization numbers, two of the numbers will be assigned to active study agent and one will be assigned to placebo. The CLO will be provided with the list of randomization numbers in blocks of 3 but will not receive the treatment assignment information. Only MRIGlobal and the study statisticians will have access to the treatment assignment information.

When a site is issued Drug Shipment Authorization and has completed study initiation, the CLO will submit a request to MRIGlobal for a block of 3 bottles of study agent to be shipped to the site. Each study participant is dispensed one bottle of study agent containing 25 tablets. Each block consists of study agent supply for 3 participants (3 bottles). The CLO will provide the site with the randomization number for a study participant after the CLO verifies the participant's eligibility. The site will then request the bottle bearing that randomization number from their pharmacy.

When a site has dispensed two of the 3 bottles in the block, the CLO will discuss shipment of another block of 3. Shipment of subsequent blocks will be determined by the number of accruals allotted to the site in their sub-award and the rate at which the site is able to accrue participants.

## **6.5 Agent Accountability**

The Investigator at each site, or a responsible party designated by the Investigator, must maintain a careful record of the inventory and disposition of all agents received from DCP using the NCI Drug

Accountability Record Form (DARF) or equivalent form. The Investigator is required to maintain adequate records of receipt, dispensing, and final disposition of study agent. Include on receipt record from whom the agent was received and to whom study agent was shipped, date, quantity, and randomization. On dispensing record, note quantities and dates study agent was dispensed to and returned by each participant.

## 6.6 Packaging and Labeling

Blinded ACTOplus met® XR/Placebo will be packaged by NCI, DCP and supplied in bottles of 25 tablets.

A two (2)-part label will be attached to each bottle of study agent. The fixed part of the label will remain attached to the bottle and will have the following identifying study specific information:

Study title: Phase IIB Randomized, Placebo-Controlled Trial of ACTOplus met® XR in Subjects with Stage I-IV Squamous Cell Carcinoma of the Oral Cavity or Oropharynx Prior to Definitive Treatment

DCP protocol number: UWI2016-07-01

Dosing Instructions: Take one (1) tablet once a day with a meal. Do not chew, cut or crush the tablets.

Recommended storage conditions: Room temperature 20–25°C (68–77°F)

Pre-generated randomization number:

Space for Participant ID number:

Space for Dispensing Date:

Caution statement: The agent is limited by United States law to investigational use only. The agent should be kept out of the reach of children.

The tear-off portion of the label will contain a scratch off area with study agent unblinding information. This portion of the label will be removed from the bottle at the time of dispensing and kept in a central location while a participant is active on the study. Upon a participant's completion of the study, if the unblinding labels were not previously stored in the participant's study binder, they should be transferred there and affixed to a source document that will be provided by the CLO in the study Visit Guides.

The tear-off portion of the label will display the following information:

Drug: Placebo or ACTOplus met® XR

Dose: 0 or pioglitazone 30 mg and metformin 1000 mg

Pre-generated randomization number:

Space for Participant ID number:

Space for Dispensing Date:

## 6.7 Storage

ACTOplus met® XR tablets should be stored at 20–25°C (68–77°F) in a secure, locked area of the research facility, with excursions permitted to 15–30°C (59–86°F). It will be dispensed in light-resistant containers.

## 6.8 Registration/Randomization

### 6.8.1 Registration:

Each participating organization (PO) will be issued a sequential list of unique participant identification (PID) numbers for this protocol. Each potential study participant will be assigned the next available PID

number from the list immediately upon signing the informed consent form (ICF) for the protocol. By signing the ICF, the candidate is considered registered to the study. The University of Wisconsin is the Consortium Lead Organization (CLO) for this protocol. The CLO must be notified of registration of a study participant within 24 hours of the participant signing the ICF.

#### 6.8.2 Randomization:

Participants who meet the eligibility criteria for the protocol will be randomized by the CLO. The PO will request randomization of a study participant by submitting (via fax or e-mail) the following documents to the CLO:

Informed Consent Form  
Eligibility Questionnaire  
Clinical safety/Eligibility lab report  
Pre-study diagnostic biopsy report  
Medical/Surgical History Worksheet

(Note: all documents submitted to the CLO must have personally identifying information deleted or completely obscured and be re-identified with the participant's PID number. Documents with visible personally identifying information will not be accepted.)

A CLO coordinator will review these documents and confirm that the participant meets the eligibility criteria and that the correct version of the ICF was signed. If eligibility is confirmed, the CLO coordinator will assign the next randomization (bottle) number in sequence for that site from a randomization list that will be pre-generated by the Statistical Center at UWCCC, as described in Section 6.4. The CLO will notify the site of the randomization number assigned to the participant. This number will correspond to the randomization number of one of the bottles of study agent issued to the site. That bottle will be requested from the site's pharmacy or other entity delegated the responsibility of study agent accountability following the site's institutional policy for requesting and dispensing study agent.

**Study agent should not be started within 48 hours following administration of an iodinated contrast agent** (commonly used in a staging CT scan). The participant's eGFR must be assessed  $\geq 48$  hours after the scan and the result must be within normal limits (see section 5.4.5) before starting study agent. To avoid missing doses of study agent (which could potentially render the participant unevaluable) if a staging test using iodinated contrast agent is planned, do not start the participant on study agent until the scan has been completed and their  $\geq 48$  hour post scan eGFR is confirmed to be within normal limits.

## 6.9 Blinding and Unblinding Methods

To ensure this trial is conducted in a double-blinded manner, the randomization code will be maintained in a password-protected database by the Statistical Center at UWCCC. Unblinding will not occur until all participants have completed the study and study data collection and analysis has been completed.

If a participant experiences a medical issue that requires knowledge of the intervention assignment for appropriate medical management, the assignment may be determined by removing the scratch-off label on the tear-off portion of the study agent bottle label. The following process should be followed:

6.9.1 The treating physician contacts the Protocol Principal Investigator, [name]. with the request to unblind.

[name]., PhD  
Associate Professor of Otolaryngology, University of Minnesota

[name]  
[name]  
[name]  
[contact]  
[contact]  
E-mail address: [[contact]](mailto:[contact])

6.9.2 The request will be approved upon the agreement of the NCI medical monitor for the protocol.

Please note: If the PI or medical monitor is unavailable to provide consent to unblind in a timely fashion, and it is in the participant's best interest not delay unblinding, the blind may be broken without waiting for PI or medical monitor consent. The following steps will still be followed:

6.9.3 The requesting site will notify the CLO ([[contact]](mailto:[contact])) immediately of the unblinding.

6.9.4 The unblinding process will be documented in the participant's study chart.

6.9.5 The participant will be removed from the study.

6.9.6 The CLO will submit formal notification that the blind has been broken to the NCI Medical Monitor.

[name]  
Chief, Lung & Upper Aerodigestive Cancer Research Group  
NCI/Division of Cancer Prevention  
[name]  
[name] (For FedEx, use [name])  
[contact]  
[contact]  
email: [[contact]](mailto:[contact])

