2	
 
No modification unless the A.E. is unacceptable to the participant or the physician feels it is in the participant's best interest medically.
 
If the A.E. may be related to dose timing, asses how the participant is dosing their study agent and if taking it at a different time of day or with a more substantial meal might help.
 
If dose modification is necessary because taking the agent with a more substantial meal did not improved the event and the participant finds it unacceptable or the physician feels it is in the participant's best interest medically, the participant may be instructed to take the study agent every other day.
 
If none of these measures is successful and the A.E. is unacceptable to the participant or the physician feels it is in the participant's best interest medically, study agent should be discontinued. However, the participant, if willing, should still be followed per the protocol schedule of events and have all study procedures conducted
 
	
 
If the A.E. may be related to dose timing, asses how the participant is dosing their study agent and if taking it at a different time of day or with a more substantial meal might help.
 
If the AE is unlikely to be related to dose timing or did not respond to taking the study agent at a different time of day or with a more substantial meal, instruct the participant to hold study agent until the AE resolves to <math>\leq</math> Grade 1 then re-start on an every-other-day dosing regimen.
 
If the AE recurs, discontinue study agent and do not re-start. However, the participant, if willing, should still be followed per the protocol schedule of events and have all study procedures conducted.
 

3	Hold study agent until consulting with the protocol's medical monitor and study chair. The medical monitor and study chair will advise whether study agent may or may not be restarted and whether a dose modification is indicated.	Discontinue study agent. Do not re-start. However, the participant, if willing, should still be followed per the protocol schedule of events and have all study procedures conducted.
4		

Hypoglycemia (The symptoms include):		
Sweating, chills and clamminess	Nervousness/shakiness/anxiety	Hunger and nausea
Irritability/impatience/confusion	Weakness/fatigue	Rapid/fast heartbeat

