### 8.3 Off-Agent Criteria

Participants may stop taking study agent for the following reasons: completed the protocol-prescribed intervention, AE or serious adverse event (SAE), inadequate agent supply, noncompliance, concomitant medications, medical contraindication, or a delay in the end of study surgical excision would place the participant out of the 25-day maximum agent dosing window. In this case, if the participant is agreeable, punch biopsies of the tumor and visually normal appearing tissue adjacent to the tumor may be obtained

in the clinic setting in lieu of during surgery. Participants will continue to be followed, if possible, for safety reasons and in order to collect endpoint data according to the schedule of events.

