## 8.4 Off-Study Criteria

Participants may go ‘off-study’ for the following reasons: the protocol intervention and any protocol-required follow-up period is completed, AE/SAE, lost to follow-up, non-compliance, concomitant medication, medical contraindication, withdraw consent, death, determination of ineligibility (including screen failure), pregnancy, or delay of surgical excision of the cancer beyond 26 days from the first dose of study agent. In the advent of such a delay, the participant will be asked if they would be willing to have punch biopsies of the tumor and visually normal appearing tissue adjacent to the tumor obtained in the clinic setting in lieu of during surgery.

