## **13.8 Evaluation of Response**

For the primary analysis comparing the absolute change in proliferation index (Ki-67) expression from baseline to post-exposure between treatment arms, an intent to treat analysis will be used. All of the participants who met the eligibility criteria, with the exception of those who did not receive study agent, will be included in the main analysis. Random dropouts will be excluded. Data will be examined for non-random dropouts. An appropriate sensitivity analysis will be conducted in the case of missing data.

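### Removing medically unblinded participants from the study (6.9.5) conflicts with the follow-up rules in 5.6 and 8.3 and the primary analysis set in 13.8, and may lose post-treatment Ki-67 tissue non-randomly

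*Combined protocol and SAP*

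**What the plan says.** Section 6.9 provides for individual unblinding: "If a participant experiences a medical issue that requires knowledge of the intervention assignment for appropriate medical management", the scratch-off label may be used. The request normally goes through the principal investigator and the medical monitor. Item 6.9.5 then gives the consequence without condition: "The participant will be removed from the study". It does not mention end-of-study tissue, safety assessments or the analysis set.

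The follow-up rules elsewhere differ. Section 5.6, on stopping agent for an adverse event, says that "the participant, if willing, should still be followed per the protocol schedule of events and have all study procedures conducted". Section 8.3, whose off-agent reasons include adverse events and medical contraindication, says: "Participants will continue to be followed, if possible, for safety reasons and in order to collect endpoint data according to the schedule of events".

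Section 8.4 lists reasons for which participants may go off study, starting with "the protocol intervention and any protocol-required follow-up period is completed, AE/SAE, lost to follow-up, non-compliance, concomitant medication, medical contraindication". Unblinding is not on the list.

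For the primary Ki-67 comparison, Section 13.8 says "an intent to treat analysis will be used". Its main analysis takes in eligible participants apart from those who never received agent, and it also drops random dropouts. Section 13.6 requires evaluable samples from before and after treatment for biomarker analyses.

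**The concern.** The protocol separates going off agent (8.3) from going off study (8.4), and for adverse events it tries to keep the participant in follow-up after agent stops. Item 6.9.5 removes that separation for one group. Two participants with the same event and the same decision to stop agent would fall under opposite rules, depending only on whether the label was scratched off.

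The primary endpoint is a within-person change, so a participant without a post-treatment tumor sample contributes nothing to it. Those whose code is broken are selected by a medical event that may be related to the assigned arm. Losing them is therefore not random dropout, and the main analysis has no rule for them.

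The loss also seems avoidable. Ki-67 is quantified by pixel counting on digital images (8.1.1), from slides cut in batches after the 18th and after the final participant complete (Section 10). Knowledge of the arm by the treating team does not reach that reading if the laboratory stays masked. In surgical participants the excised tumor is paraffin-embedded as part of routine care (7.6.1).

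**Working it through.** **1. The rules side by side, for a participant with a medical event during dosing**

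- Agent stopped, code intact (5.6, 8.3): followed to the end of the schedule if willing or possible, endpoint data included.
- Code broken (6.9.5): removed from the study, with no conditional wording.
- Off-study list (8.4): permissive; it includes AE/SAE and medical contraindication but not unblinding.
- Primary analysis (13.8): if eligible and dosed, included; unblinding is not an exception.
- Biomarker data (13.6): included only if both samples are evaluable.

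So 13.8 expects the unblinded participant in the analysis, while 6.9.5 may stop collection of the sample that 13.6 requires.

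**2. What is and is not at risk**

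- Adverse-event data: kept. Everyone dosed is in the toxicity analysis (13.6, 13.7), and serious events are followed to resolution (11.2.3).
- Scheduled end-of-study exam and labs: uncertain. The Schema and Section 7.1 have a combined End of Study or Early Termination visit, but 6.9.5 does not refer to it.
- Post-treatment tumor tissue: uncertain. That visit includes biopsies. However, for participants whose baseline sample came from a direct laryngoscopy biopsy, Section 4.1.2 says end-of-study tissue can be obtained only at their standard surgical excision. A clinic termination visit cannot supply it.

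**3. The plan's own power figures**

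Inputs from 13.3: 24 active, 12 placebo, two-sided alpha 0.05.

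- Equivalent n per arm = 1/{[1/24 + 1/12]/2} = 1/0.0625 = 16.
- Detectable effect size = (z for alpha + z for power) × √(2/16).
- Power 0.80: (1.960 + 0.842) × 0.3536 = 0.991 (plan: 1.00).
- Power 0.85: 1.059 (plan: 1.06). Power 0.90: 1.146 (plan: 1.15).

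The table reproduces. At effect size 1.00 the normal approximation gives power 0.807.

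**4. Cost of losing one or two participants below 24/12**

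The number lost is an assumption, since the documents give no unblinding rate. Exact two-sample t power uses noncentrality = 1.00/√(1/n₁ + 1/n₂) and n₁ + n₂ − 2 degrees of freedom.

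| Active / placebo | Noncentrality | Exact t power | Normal approximation |
|---|---|---|---|
| 24 / 12 | 2.828 | 0.785 | 0.807 |
| 23 / 12 | 2.808 | 0.778 | 0.802 |
| 24 / 11 | 2.746 | 0.760 | 0.784 |
| 22 / 12 | 2.787 | 0.771 | 0.796 |
| 24 / 10 | 2.657 | 0.731 | 0.757 |

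One loss costs 0.785 − 0.778 = 0.007 (active) or 0.785 − 0.760 = 0.025 (placebo). Enrollment is 39, so 39 − 36 = 3 unevaluable participants are already budgeted (Section 3, 13.3). These costs arise only once that allowance is used up.

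**5. Possible bias, for scale only**

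If k of n participants in an arm are lost and their mean change differs from the rest by d SD, the observed arm mean is off by (k/n) × d. With an assumed d = 1, two of 24 active gives 2/24 = 0.083 SD and one of 24 gives 0.042 SD, against a detectable effect of about 1.00 SD. Nothing in the documents supports a particular value of d.

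**The case against.** The strongest reply is that 6.9.5 is terse rather than destructive. It says nothing about discarding tissue or skipping labs, and the schedule has an Early Termination visit with exam, labs, event review and biopsies that sites could apply. Section 8.4 already lets participants leave the study for an adverse event or medical contraindication. Section 13.8 is not strict intention to treat and promises to look for non-random dropout, with a sensitivity analysis for missing data. Dosing lasts at most 25 days and code breaks need a medical reason, so there may be none.

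Much of this stands. A reader might infer that unblinded participants' tissue and safety data are lost. The documents do not support that: loss of tissue is possible but not stated, and adverse-event analysis and serious-event follow-up continue. A reader might also infer a direct breach of intention to treat. But 6.9.5 excludes nobody from analysis, and an unblinded participant with both samples would be counted under 13.6.

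The conflict remains. Section 8.4 is permissive and omits unblinding, whereas 6.9.5 is mandatory. It does not send the participant to the Early Termination visit, and that visit cannot provide tissue for the laryngoscopy group. The sensitivity analysis in 13.8 has no stated method, and it is a weaker remedy than collecting a sample the protocol already schedules.

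**Conclusion.** The point holds as a conflict between 6.9.5 and Sections 5.6, 8.3 and 13.8, with 8.4 silent. Followed literally, 6.9.5 may cause avoidable, non-random loss of the post-treatment Ki-67 value. It does not remove participants from the adverse-event analysis; on the safety side only the scheduled end-of-study exam and labs are in doubt.

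The expected effect is small and could be nil. The power loss of 0.007 or 0.025 assumes one code break, loss of that participant's tissue, and a loss allowance already spent. The shift of 0.042 to 0.083 SD also assumes a 1 SD difference. The case for acting is that the conflict is plain, the placebo arm has only 12 planned evaluable participants, and the repair is cheap.

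**What to change.** Reconcile 6.9.5 with 5.6, 8.3, 8.4, 13.6 and 13.8. State that:

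- breaking the code does not in itself end data collection;
- the end-of-study tissue and safety assessments already in the schedule are obtained if the participant is willing;
- the participant is analysed in the assigned arm, with the unblinding flagged;
- the tissue laboratories stay masked to assignment.

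Whether study agent continues after a code break is a clinical matter. Sections 5.6 and 6.9 do not settle it together, and the sponsor should reconcile them.

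The cost is one sentence of protocol text and a flag in the data. No procedure is added beyond the current schedule. For non-surgical participants the end-of-study biopsy is a research procedure, so the condition that the participant is willing should be explicit.

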## **6.10 Agent Destruction/Disposal**

DCP-supplied agents: at the completion of investigation, all unused study agent will be returned to NCI, DCP Repository according to the DCP "Guidelines for AGENT RETURNS" and using the DCP form "Return Drug List".

The Guidelines and form are available on the DCP website.

